#### Table 2. Dose Adjustment Rules: Monthly, Weekly, and Withholding in Subjects < 2 Years old

\* restart one PSD below last dose when cCa is > 9.0 mg/dL, iPTH is > 150 pg/mL, ionized calcium is > 1.13 mmol/L symptoms of hypocalcemia and other AE that warrants IP dose withholding have resolved.

\*\* if any lab values that warrant a dose decrease are received between regularly scheduled visits, the subject dose should be suspended until the next visit, at which time the dose will be decreased.

CONFIDENTIAL

Page 33 of 79

#### 6.2.3.1.2.2 Subjects ≥ 2 Years of Age

The initial dose of cinacalcet and all subsequent doses will be calculated by the site staff and confirmed by the IVR/IWR system.

For subjects with > 14 days since the last dose of cinacalcet in Study 20110100 and day 1 of Study 20140159, subjects will start at the initial cinacalcet dose of 0.20 mg/kg/day, based on the subject's dry weight at day 1 in Study 20140159, rounded down to the lowest PSD.

For subjects with  $\leq$  14 days since the last dose of cinacalcet in Study 20110100 and day 1 of Study 20140159, subjects will continue cinacalcet based on the dose at the EOIP visit or early termination/EOS at study termination and follow the weekly dose adjustments outlined in Table 3. Dose titration cannot occur until week 4. If subjects from the Study 20110100 are on a dose that was withheld at day 1 of Study 20140159, the iPTH and cCa restart values (iPTH > 150 pg/mL and cCa > 8.4 mg/dL) must be reached before resuming cinacalcet in Study 20140159.

Dose adjustments for subjects receiving cinacalcet will be assessed at each weekly visit during the treatment period. The daily dose of cinacalcet may only be increased at monthly titration visits (week 4, 8, 12, 16, 20, and 24); it can't be increased at any other time during the treatment period. At all weekly visits (including week 4, 8, 12, 16, 20, and 24), the dose may be maintained, reduced or withheld based upon the criteria in Table 3.

If any of the criteria for dose withholding are met at any time during the trial, including between scheduled study visits (ie, unscheduled), the dose of cinacalcet is to be withheld until all of the following criteria are met:

- central laboratory corrected calcium value is >8.4 mg/dL
- iPTH is >150 pg/mL
- ionized calcium is >1.05 mmol/L
- subject has no symptoms of hypocalcemia
- subject doesn't have any ongoing adverse event(s) which warrant withholding of cinacalcet.

If a subject dose is being withheld, ionized calcium levels should be assessed weekly until an ionized calcium of >1.05 mmol/L is obtained, at which point, cCa and iPTH should be assessed by the central laboratory.

**AMGEN**®

Page 34 of 79

Page 35 of 79

Once all the restart criteria above are met, cinacalcet may be restarted at one PSD below the previous dose received. Subjects receiving the lowest PSD (1 mg) who require a dose reduction will have their dose withheld until the criteria for maintaining or increasing the dose are met, at which time they will restart dosing at 1 mg/day.

If subjects require temporary administration of concomitant medications that are known to prolong the QTc interval, are CYP3A4 inhibitors, or are CYP2D6 substrates, the administration of IP is to be withheld. The dose may be restarted at one PSD below the previous dose once the treatment with the concomitant medication has completed and all of the restart criteria above are met.

If IP has been withheld or missed for more than 14 days (initial dose in parent Studies 20130356 or 20110100), the subject will resume dosing at the starting dose level once all restart criteria are met.

If any of the criteria for dose decrease are met between scheduled study visits, the dose of cinacalcet is to be suspended until the next visit at which time the dose will be decreased per dose adjustment procedures of that visit.

CONFIDENTIAL

Product: Cinacalcet HCI Protocol Number: 20140159 Date: 01 June 2016 Page 36 of 79

			itration Visit Rules 12, 16, 20, 24)	i -	(Weeks 1, 2	ose Adjustment V 2, 3, 5, 6, 7, 9, 10 3, 19, 21, 22, 23, 2	, 11, 13, 14,	Dose Withholding for Safety at Any Time (Monthly, Weekly or Unscheduled)
	↑ one PSD	Maintain Dose	↓ one PSD**	withhold*	Maintain Dose	↓ one PSD**	withhold*	withhold*
	(if all  criteria met)	(if al l criteria met)	(if any criteria met)	(if any criteria met)	(if al l criteria met)	(if any criteria met)	(if any criteria met)	(if any criteria met)
Corrected Calcium (central laboratory)	≥ 8.4 mg/dL	≥8.4 mg/dL	≥ 8.0 - < 8.4 mg/dL	< 8.0 mg/dL	≥ 8.4 mg/dL	≥ 8.0 - < 8.4 mg/dL	< 8.0 mg/dL	< 8.0 mg/dL
	(≥ 2.1 mmol/L)	(≥2.1 mmol/L)	(≥ 2.0- < 2.1 mmol/L)	(< 2.0 mmol/L)	(≥ 2.1 mmol/L)	(≥ 2.0- < 2.1 mmol/L)	(< 2.0 mmol/L)	(< 2.0 mmol/L)
Ionized Calcium	≥ 1.05 mmol/L	≥ 1.05 mmol/L	≥ 1.00 - < 1.05 mmol/L	< 1.00 mmol/L	≥ 1.05 mmol/L	≥ 1.00 - < 1.05 mmol/L	< 1.00 mmol/L	< 1.00 mmol/L
Total Calcium (local laboratory)	N/A	N/A	N/A	< 8.0 mg/dL (< 2.0 mmol/L)	N/A	N/A	< 8.0 mg/dL (< 2.0 mmol/L)	< 8.0 mg/dL (< 2.0 mmol/L)
iPTH	≥ 300 pg/mL	≥ 150 - < 300 pg/mL	≥ 100 - < 150 pg/mL	< 100 pg/mL	≥ 150 pg/mL	≥ 100 - < 150 pg/mL	< 100 pg/mL	< 100 pg/mL
	(≥ 31.8 pmol/L)	(≥ 15.9 - < 31.8 pmol/L)	(≥ 10.6 - < 15.9 pmol/L)	(< 10.6 pmol/L)	(≥ 15.9 pmol/L)	(≥ 10.6 - < 15.9 pmol/L)	(< 10.6 pmol/L)	(< 10.6 pmol/L)
Symptoms of Hypocalcemia	None	None	N/A	Yes	None	N/A	Yes	Yes
Other AE that warrants IP dose withhold	None	None	N/A	Yes	None	N/A	Yes	Yes

#### Table 3. Dose Adjustment Rules: Monthly, Weekly, and Withholding in Subjects ≥ 2 Years old in Study 20110100

\* restart one PSD below last dose when cCa is > 8.4 mg/dL, iPTH is > 150 pg/mL, ionized calcium is > 1.05 mmol/L, symptoms of hypocalcemia and other AE that warrants IP dose withholding have resolved.

\*\* if any lab values that warrant a dose decrease are received between regularly scheduled visits, the subject dose should be suspended until the next visit, at which time the dose will be decreased per dose adjustment procedures of that visit.

If a subject misses > 14 consecutive doses of cinacalcet for any reason, including temporary dose withholding due to the administration of concomitant medications as noted above, they will be restarted at their initial dose of cinacalcet (0.20 mg/kg/day based on dry weight at day 1 in Study 20140159) when administration of IP resumes per the dose titration guidelines outlined in Table 1, Table 2, and Table 3.

#### 6.2.3.2 Measures of Compliance With Cinacalcet Administration

Poor compliance and/or intermittent dosing or ingestion of cinacalcet may lead to changes (ie, increases or decreases) in iPTH and calcium concentrations that do not conform to those seen in clinical trials where subjects have consistently received daily doses of cinacalcet. Increases in iPTH can be interpreted to be a result of subtherapeutic dosing leading to increases in cinacalcet doses which may result in potentially severe hypocalcemia, particularly in the setting of intermittent ingestion of IP.

Electronic patient diaries (eDiary) and IP accountability information will be reconciled and utilized in this study to document subject compliance with daily administration of cinacalcet therapy. The data entered into the eDiary will be available to the investigator and/or study coordinator on a daily basis to enable ongoing reviews of subject compliance. The eDiary and IP accountability data collected will be reviewed with the subject and/or their parent(s) or legal guardian(s) by the investigator and/or study coordinator during the weekly study visits.

For this study non-compliance is defined as:

- missing > 2 doses within any dosing week, or
- ≥ 2 documented overdoses within a dosing week
- other indicators of non-compliance per physician judgment

If a subject is considered to be non-compliant, the dose of cinacalcet should not be increased and additional counseling should be provided about the importance of taking the study medication as prescribed. It will also be documented on the eCRF. The additional counseling should be documented in the subject's source documents. If the subject remains non-compliant, removal from IP dosing should be considered.

### 6.2.3.3 Overdose

An overdose of cinacalcet will be defined as receiving any dose greater than the assigned daily dose. This can cause hypocalcemia. Hypocalcemia may cause anxiety, muscular cramping or stiffness, twitching, tingling, paresthesias around the mouth or

**AMGEN**®

Page 37 of 79

extremities, tetany, abdominal cramping, arrhythmias, hypotension, worsening of pre-existing chronic heart failure, convulsions, or death.

If an overdose is suspected, the Amgen Study Manager, Amgen Medical Monitor, and/or Amgen Clinical Safety representative should be contacted within 24 hours of discovery. For subjects in whom an overdose is suspected, close monitoring for signs and symptoms of hypocalcemia and appropriate measures (eg, including intravenous calcium gluconate and more frequent monitoring of calcium levels) should be considered by the investigator in those with acute symptomatic hypocalcemia.

Once hypocalcemia and any symptoms associated with the overdose have resolved, subjects resume cinacalcet administration dose. To resume dosing, the subject must meet the dosing restart criteria for his/her respective age group as specified in Sections 6.2.3.1.1, 6.2.3.1.2.1, and 6.2.3.1.2.2.

#### 6.3 Hepatotoxicity Stopping and Rechallenge Rules

Subjects with abnormal hepatic laboratory values (ie, alkaline phosphatase [ALP], aspartate aminotransferase [AST], alanine aminotransferase [ALT], total bilirubin [TBL]) and/or international normalized ratio (INR) and/or signs/symptoms of hepatitis (as described below) may meet the criteria for withholding or permanent discontinuation of Amgen IP or other protocol-required therapies as specified in the Guidance for Industry Drug-Induced Liver Injury: Premarketing Clinical Evaluation, July 2009.

Cinacalcet is metabolized by the liver. Subjects with moderate to severe hepatic impairment have the potential for 2- to 4-fold higher area under the curve (AUC) of cinacalcet concentration and may require additional follow-up.

#### 6.3.1 Criteria for Permanent Discontinuation of Amgen Investigational Product and Other Protocol-required Therapies Due to Potential Hepatotoxicity

Cinacalcet should be discontinued permanently and the subject should be followed according to the recommendations in Appendix A (Additional Safety Assessment Information) for possible drug-induced liver injury (DILI), if ALL of the criteria below are met:

- TBL > 2 × upper limit of normal (ULN) or INR > 1.5
- AND increased AST or ALT from the relevant day 1 value as specified below:

Baseline AST or ALT value	AST or ALT elevation	
< ULN	> 3 × ULN	

CONFIDENTIAL

**AMGEN**®

- AND no other cause for the combination of the above laboratory abnormalities is immediately apparent; important alternative causes for elevated AST/ALT and/or TBL values include, but are not limited to:
- Hepatobiliary tract disease
- Viral hepatitis (eg, Hepatitis A/B/C/D/E, Epstein-Barr Virus, cytomegalovirus, Herpes Simplex Virus, Varicella, toxoplasmosis, and Parvovirus)
- Right sided heart failure, hypotension or any cause of hypoxia to the liver causing ischemia.
- Exposure to hepatotoxic agents/drugs or hepatotoxins, including herbal and dietary supplements, plants and mushrooms
- Heritable disorders causing impaired glucuronidation (eg, Gilbert's Syndrome, Crigler-Najjar syndrome) and drugs that inhibit bilirubin glucuronidation (eg, indinavir, atazanavir)
- Alpha-one antitrypsin deficiency
- Alcoholic hepatitis
- Autoimmune hepatitis
- Wilson's disease and hemochromatosis
- Nonalcoholic Fatty Liver Disease including Steatohepatitis (NASH)
- Non-hepatic causes (eg, rhabdomylosis, hemolysis)

If an alternative cause for hepatotoxicity is identified or less stringent conditions developed than what are noted above, determine (based on patient population and/or severity of the hepatotoxicity or event) if Amgen IP and other protocol-required therapies should be withheld (see section 6.3.2) or permanently discontinued, as deemed appropriate for the safety of the subject.

Page 39 of 79

AMGEN

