#### 4.1.2 Exclusion Criteria

General

Studies 20130356 or 20110100

- 201 Currently receiving treatment in another investigational device or drug study, or less than 30 days since ending treatment on another investigational device or drug study(s), other than Amgen Studies 20130356 or 20110100.
- 202 Other investigational procedures while participating in this study are excluded.
- 203 Malignancy except non-melanoma skin cancers, cervical or breast ductal carcinoma in situ within the last 5 years.
- 204 Subject has known sensitivity to any of the products to be administered during dosing.
- 205 Subject likely to not be available to complete all protocol-required study visits or procedures, and/or to comply with all required study procedures (eg, electronic patient diary [ediary]) to the best of the subject and investigator's knowledge
- 206 History or evidence of any other clinically significant disorder, condition or disease (with the exception of those outlined above) that, in the opinion of the investigator or Amgen physician, if consulted, would pose a risk to subject safety or interfere with the study evaluation, procedures, or completion.
- 207 Subject previously has entered this study.
- 208 If sexually active, subject is not willing to use acceptable contraception during treatment and for at least 9 days after the end of treatment.
- 209 Subject is pregnant or breast feeding, or planning to become pregnant during the study or within 9 days after the end of treatment
- 210 History of congenital long QT syndrome, second or third degree heart block, ventricular tachyarrythmias, or other conditions associated with prolonged QT interval

Page 22 of 79

211 A new onset of seizures or worsening of pre-existing seizure disorder

All Subjects with > 14 days between the last study visit in Study 20130356 or Study 20110100 and the screening visit in Study 20140159 will have the following exclusion criteria applied during screening and day 1:

- 212 Unstable chronic heart failure defined as worsening pulmonary edema or other signs and symptoms as per investigator assessment during screening
- 213 Received therapy with commercial cinacalcet after the last study visit in Study 20130356 or Study 20110100 before day 1 of Study 20140159
- 214 Scheduled date for kidney transplantation from a known living donor that makes completion of the study unlikely

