- 215 Either new or recurrent cardiac ventricular arrhythmias requiring a change in treatment within 10 days prior to screening visit or day 1 of Study 20140159 screening
- 216 Hepatic impairment indicated by elevated levels of hepatic transaminase or bilirubin (aspartate aminotransferase [AST] ≥ 1.5 × upper limit of normal [ULN] OR alanine aminotransferase [ALT] ≥ 1.5 × ULN OR total bilirubin ≥ 1 × ULN per institutional laboratory range) during screening

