# ional Withholding of Amgen Investigational

#### 6.3.2 Criteria for Conditional Withholding of Amgen Investigational Product and Other Protocol-required Therapies Due to Potential Hepatotoxicity

For subjects who do not meet the criteria for permanent discontinuation of Amgen IP outlined above and have no underlying liver disease, and eligibility criteria requiring normal transaminases and TBL at baseline or subjects with underlying liver disease and baseline abnormal transaminases, the following rules are recommended for withholding of Amgen IP and other protocol-required therapies:

	5 5
Baseline AST or ALT value	AST or ALT elevation
Any	> 8 × ULN at any time
Any	> 5 × ULN but < 8 × ULN for $\ge$ 2 weeks
Any	> 5 × ULN but < 8 × ULN and unable to adhere to enhanced monitoring schedule
Any	> 3 × ULN with clinical signs or symptoms that are consistent with hepatitis (such as right upper quadrant pain/tendemess, fever, nausea, vomiting, jaundice).

• Elevation of either AST or ALT according to the following schedule:

- OR: TBL > 3 × ULN at any time
- OR: ALP > 8 × ULN at any time

Cinacalcet should be withheld pending investigation into alternative causes of DILI. If investigational product(s) is withheld, the subject is to be followed according to recommendations in Appendix A for possible DILI. Rechallenge may be considered if an alternative cause for impaired liver tests (ALT, AST, ALP) and/or elevated TBL, is discovered and the laboratory abnormalities resolve to normal or baseline (Section 6.3.3).

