## 6.3.3 Criteria for Rechallenge of Amgen Investigational Product and Other Protocol-required Therapies After Potential Hepatotoxicity

The decision to rechallenge the subject should be discussed and agreed upon unanimously by the subject's legally acceptable representative(s), investigator, and Amgen.

If signs or symptoms recur with rechallenge, then cinacalcet should be permanently discontinued. Subjects who clearly meet the criteria for permanent discontinuation (as described in Section 6.3.1) should never be rechallenged.

Page 40 of 79

CONFIDENTIAL

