# Drug-induced Liver Injury Reporting & Additional Assessments

#### Reporting

To facilitate appropriate monitoring for signals of DILI, cases of concurrent AST or ALT and TBL and/or INR elevation according to the criteria specified in Section 6.3 require the following:

- The event is to be reported to Amgen as a serious adverse event within 24 hours of discovery or notification of the event (ie, before additional etiologic investigations have been concluded)
- The appropriate CRF (eg, Adverse Event CRF) that captures information necessary to facilitate the evaluation of treatment-emergent liver abnormalities is to be completed and sent to the Amgen.

Other events of hepatotoxicity and potential DILI are to be reported as serious adverse events if they meet the criteria for a serious adverse event defined in Section 9.1.2.

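### The permanent-discontinuation liver rule in Section 6.3.1 appears to have no AST/ALT criterion for subjects who enter with both enzymes at or above ULN

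*Protocol*

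**What the plan says.** Protocol Section 6.3.1 sets the permanent stop for possible drug-induced liver injury. All three of its conditions must hold: TBL above 2 × ULN or INR above 1.5; "AND increased AST or ALT from the relevant day 1 value as specified below"; and no other immediately apparent cause. The table that gives the enzyme criterion shows one row, for a baseline value below ULN and an elevation above 3 × ULN. The closing paragraph of 6.3.1 covers other situations by judgment. If another cause is found, or "less stringent conditions developed than what are noted above, determine (based on patient population and/or severity of the hepatotoxicity or event"), the decision is whether to withhold or to discontinue permanently.

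Section 6.3.3 ties a further consequence to the stop: "Subjects who clearly meet the criteria for permanent discontinuation (as described in Section 6.3.1) should never be rechallenged".

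On entry, Section 4.1.2 has one numeric liver criterion: "216 Hepatic impairment indicated by elevated levels of hepatic transaminase or bilirubin", set at AST or ALT ≥ 1.5 × ULN or total bilirubin ≥ 1 × ULN. It belongs to the group introduced by "will have the following exclusion criteria applied during screening and day 1", which covers only subjects with more than 14 days between the last parent-study visit and screening.

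Section 6.3.2, on conditional withholding, is written for subjects with "eligibility criteria requiring normal transaminases and TBL at baseline or subjects with underlying liver disease and baseline abnormal transaminases". All its AST/ALT rows apply to any baseline.

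**The concern.** The stopping rule is keyed to the day 1 value, but only one category of day 1 value is listed. Because every condition must be met, a subject with both enzymes at or above ULN on day 1 cannot satisfy the rule, however high the enzymes, bilirubin or INR later go. Section 6.3.2 shows that the authors expected some abnormal baselines, and the entry criteria let such subjects in.

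If the table is complete, following the protocol as written gives the weaker rule to the child who entered with the worse liver tests. That child loses the recommended permanent stop and the linked bar on rechallenge. Section 6.3 itself notes that moderate to severe hepatic impairment can raise cinacalcet exposure 2- to 4-fold, and drug-related hepatic disorders are among the events of interest in the primary endpoint. This is a gap in a safety rule. It changes no statistical figure.

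**Working it through.** The plan states no figure to reproduce here, so the check is one of logic. Enzymes and TBL are in multiples of ULN, and m is the larger of on-study ALT and AST.

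**Inputs**
- 6.3.1 stop: (TBL > 2 or INR > 1.5), and (day 1 ALT < 1 with ALT > 3, or day 1 AST < 1 with AST > 3), and no other cause.
- 6.3.2 withholding, any baseline: m > 8; or m > 5 and < 8 for at least 2 weeks; or "> 5 × ULN but < 8 × ULN and unable to adhere to enhanced monitoring schedule"; or m > 3 with hepatitis-type symptoms; or TBL > 3; or ALP > 8.
- Appendix A close observation: m > 3.
- Criterion 216: excludes AST or ALT ≥ 1.5 or TBL ≥ 1, only when the gap exceeds 14 days.

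**Step 1: can such subjects enter?** With both enzymes from 1.0 to below 1.5 and bilirubin below ULN, criterion 216 excludes no one at a gap of 7 or 20 days. With both at 2.0, the subject is excluded at 20 days but not at 7. Direct roll-overs face no numeric enzyme limit in this protocol. They face only criterion 206 (investigator or sponsor-physician judgment) and criterion 217 (an ongoing adverse event related to investigational product that is grade 3 or higher, or clinically significant).

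**Step 2: which rule applies on study?** The illustrative profiles assume no other cause and ALP ≤ 8, with no symptoms and monitoring followed unless stated. The 6.3.2 column shows whether its thresholds are reached.

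| On-study ALT/AST/TBL | 6.3.1, day 1 ALT/AST 0.9/0.9 or 0.9/1.1 | 6.3.1, day 1 1.2/1.1 or 1.4/1.4 | 6.3.2 thresholds, any day 1 |
|---|---|---|---|
| 4/3.5/2.5 | met | not met | not met |
| 7/6/2.5, 1 week | met | not met | not met |
| 7/6/2.5, 2 weeks | met | not met | met |
| 9/7/2.5 | met | not met | met |
| 4/3.5/2.5 with vomiting | met | not met | met |
| 4/3.5/3.2 | met | not met | met |

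Close observation applies in all 6 × 4 = 24 combinations. The INR route behaves the same way. At ALT and AST 4, TBL 1 and INR 1.6, day 1 values of 0.8/0.8 meet 6.3.1, while both enzymes at or above ULN meet neither rule. One enzyme below ULN on day 1 is enough to keep 6.3.1 reachable, so the gap needs both raised.

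**Step 3: where does no numeric rule apply?** Both enzymes must be at or above ULN on day 1, with no symptoms, no other cause and ALP ≤ 8. Then neither rule applies when
- m is > 3 to 5, or > 5 to < 8 for under 2 weeks with monitoring followed; and
- TBL is > 2 to 3, or INR > 1.5 with TBL ≤ 3.

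**Step 4: does a plain extra row work?** With the row 'baseline ≥ ULN: > 3 × ULN', the patterns in step 2 meet 6.3.1 at every day 1 pair. For a day 1 value b, exceeding 3 means a rise of more than 3/b: 3/1.2 = 2.5-fold and 3/1.5 = 2-fold. So up to 1.5 × ULN the row already demands at least a doubling. Above that it weakens: 3/2.0 = 1.5-fold, and a trivial rise from 2.9 to 3.1 (3.1/2.9 = 1.07) would count.

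Also requiring a multiple k of the day 1 value sets the threshold at max(3, k × b):

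| k | b = 1.2 | b = 2.0 | b = 2.9 |
|---|---|---|---|
| 1.5 | 3 | 3 | 4.35 |
| 2 | 3 | 4 | 5.8 |
| 3 | 3.6 | 6 | 8.7 |

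A multiple has a price. At k = 2 and b = 2.0, ALT 3.5 with TBL 2.5 still falls short of 4. At k = 3 and b = 2.9, 8.7 exceeds the 8 × ULN level at which 6.3.2 already withholds.

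**The case against.** The strongest reply is that the table may be incomplete only in this copy. The single row falls at a page break, neighbouring text in 6.3.2 is visibly disordered, and a table headed by baseline value with one category is what a lost row would look like. This stands, and only the source page can settle it. Against it, the row is complete in itself, the 6.3.2 table kept its four rows, and no other section or amendment entry gives a criterion for raised baselines. The amendment log shows only that the table was not changed.

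The second reply is that raised baselines were left to judgment on purpose. The closing paragraph of 6.3.1 does allow permanent discontinuation at discretion. Protection at any baseline is substantial. Appendix A requires repeat tests, including bilirubin and INR, within 24 hours once AST or ALT exceeds 3 × ULN. Section 6.3.2 withholds at its own thresholds, and Tables 1 to 3 allow withholding for another adverse event. After 6.3.2 withholding, rechallenge needs an alternative cause, resolved tests and unanimous agreement. All of this limits the harm. It does not explain why identical on-study results should lead to a stated stop for one child and to judgment for another, across about 60 sites.

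A reader might infer three stronger points that the documents do not support.
- That a mandatory stop is missing: 6.3.1 says the drug should be discontinued, so what is lost is a recommended stop.
- That these subjects have no liver protection: the provisions just listed apply to them.
- That expedited reporting is lost: Appendix A refers to "cases of concurrent AST or ALT and TBL and/or INR elevation according to the criteria specified in Section 6.3 require the following". It cites Section 6.3 as a whole, although only 6.3.1 sets out that combination, so the trigger is unclear but not absent. Section 9.1.2 also names drug-induced liver injury as an example of a medically important serious event, and Section 9.2.2 requires every serious event to reach the sponsor within 24 hours.

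**Conclusion.** The point holds, conditional on the source page showing no second row. For a subject with both enzymes at or above ULN on day 1, the 6.3.1 stop and the 6.3.3 bar on rechallenge cannot be triggered. In the band derived in step 3, no numeric stop or withhold rule applies at all. Outside that band, 6.3.2 may recommend withholding, but 6.3.1 still cannot be met.

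The number affected is unknown and probably small. At most 78 subjects enroll, both enzymes must be raised on day 1, and the parent studies' hepatic exclusions are not in these documents. Section 6.3 also cites an external guidance on drug-induced liver injury; its content is not available here and cannot be assumed to fill the gap. The sponsor should correct this because a written rule gives the weaker instruction to the subject with worse entry tests, and the repair is small.

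**What to change.** First check the original page for a row lost at the break. If one is there, no change to the stopping rule is needed.

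If not, add one row to the 6.3.1 table: baseline at or above ULN, elevation above 3 × ULN. No multiple is needed for day 1 values up to 1.5 × ULN. Day 1 values above that can occur only in direct roll-overs, because criterion 216 removes them after a longer gap. For those subjects the sponsor's hepatic-safety lead should decide whether to require a multiple of the day 1 value as well. The documents give no multiple; the 1.5 to 3 range above is an assumption that shows the trade-off. In the same amendment, bring the 6.3.2 wording about normal baseline transaminases into line with Section 4.1.2, which does not require them of all subjects.

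The cost is one table row and one phrase. Liver tests are already drawn on day 1, so no procedure is added. The downside is an occasional extra permanent discontinuation in a subject who entered with raised enzymes.
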